# 15.6.4 Confidentiality

Confidentiality of subject's information must be maintained in accordance with local privacy laws.

# 15.6.5 ClinicalTrials.gov

This study has been listed with ClinicalTrials.gov, as required.

# 15.6.6 Termination of Study

The Sponsor reserves the right to suspend or discontinue this study for administrative and/or safety reasons at any time. The PI reserves the right to discontinue dosing subjects at any time for safety reasons.

#### 15.7 Data Handling and Record Keeping

The PI must maintain all documentation related to this study. All essential documents (as defined in the ICH Guideline E6) and the data generated in connection with this study, together with the original copy of the final report, will be retained for at least 5 years after the last approval of a marketing application in an ICH region and until there are no pending or contemplated marketing applications in an ICH region or at least 5 years have elapsed since the formal discontinuation of clinical development of the investigational product. These documents should be retained for a longer period if required by the applicable regulatory requirements or by an agreement with the Sponsor.

It is the responsibility of the Sponsor to inform the PI/Institution as to when these documents no longer need to be retained.

# 15.8 Protocol Amendments

Amendments to the study protocol may occur as the study progresses. Amendment(s) will be approved and signed off in the same way as the protocol.

# 15.9 Report Format

According to the ICH Harmonized Tripartite Guideline (Organization of the Common Technical Document for the Registration of Pharmaceuticals for Human Use M4 and the ICH M2 Expert Working Group), the final report will be written according to the ICH E3 Guideline (Structure and Content of Clinical Study Reports).

# 15.10 Finance and Insurance

Finance and insurance will be addressed in a Clinical Trial Agreement between the PI/Institution and the Sponsor.

# 15.11 Publication Policy

The data generated for this study are considered confidential information and are the property of the Sponsor. All study information provided to the PI and Site personnel by the Sponsor shall not be published or disclosed to a third party without the prior written consent of the Sponsor.

After the completion of the study, the data may be reported at a scientific meeting and/or submitted for publication in a scientific journal with the prior written consent of the Sponsor. The Sponsor must be given at a minimum 30 days to review the materials to be presented at a scientific meeting and/or for publication in a scientific journal.

# **REVISION HISTORY**

Version No.	Version Date	Description of Modifications
1.0	27 Apr 2020	Original Document

# 1. LIST OF ABBREVIATIONS AND ACRONYMS

Abbreviations and	Description
Acronyms	
°C	Degrees Celsius
ADaM	Analysis Data Model
ADDV	ADaM Data Structure for Protocol Deviation Analysis
ADPC	ADaM Data Structure for Pharmacokinetic Concentrations
	Analysis
ADPP	ADaM Data Structure for Pharmacokinetic Parameters
	Analysis
AE	Adverse Event
AESI	Adverse Event of Special Interest
AIHA	Autoimmune Hemolytic Anemia
ATC	Anatomical Therapeutic Chemical
CAD	Cold Agglutinin Disease
BLQ	Below the Limit of Quantification
bpm	beats per minute
CFB	Change From Baseline
Ctrough, max	Maximal Trough Concentration
CS	Clinically Significant Abnormality
DPC	DP Clinical Inc.
ECG	Electrocardiogram
eCRF	Electronic Case Report Form
ET	Early Termination
ETFU	Early Termination Follow-up
FACIT	Functional Assessment of Chronic Illness Therapy
HiB	Haemophilus Influenzae Type B
ICH	International Council for Harmonisation of Technical
	Requirements for Pharmaceuticals for Human Use
ITT	Intent-to-Treat
LASA	Linear Analog Scale Assessment
LDH	Lactate Dehydrogenase

Version 1.0

27 Apr 2020

Abbreviations and	Description
Acronyms	
LLOQ	Lower Limit of Quantification
MedDRA	Medical Dictionary for Regulatory Activities
mmHg	Millimeters of Mercury
msec	Milliseconds
NCS	Not Clinically Significant
ODS	Output Delivery System
QC	Quality Control
QoL	Quality of Life
QtC	Corrected QT interval
QTcB	Bazett's QT Interval Correction
QTcF	Fridericia's QT Interval Correction
PRBC	Packed Red Blood Cell
PCFB	Percent Change From Baseline
PCV13	Pneumococcal Conjugate Vaccine
PD	Pharmacodynamics
PI	Principal Investigator or Designee
РК	Pharmacokinetics
PP	Per Protocol
PPSV23	Pneumococcal Polysaccharide Vaccine 23
PT	Preferred Term
RBC	Red Blood Cell
RTF	Rich Text Format
SAE	Serious Adverse Event
SAP	Statistical Analysis Plan
SC	Subcutaneous
SD	Standard Deviation
SDTM	Study Data Tabulation Model
SOC	System Organ Class
SOP	Standard Operating Procedure
TEAE	Treatment-Emergent Adverse Event
TLFs	Tables, Listings and Figures

Version 1.0

Abbreviations and	Description
Acronyms	
wAIHA	Warm Antibody Autoimmune Hemolytic Anemia
WHO	World Health Organization
WHODrug	World Health Organization Drug Dictionary
WOCBP	Woman of Childbearing Potential

# 2. INTRODUCTION

This Statistical Analysis Plan (SAP) is prepared to provide a more technical and detailed elaboration of the principal statistical features stated in the protocol. The SAP will ensure that the tables, listings, and figures that will be produced and statistical methods that will be used are complete and accurate and will allow valid conclusions to be drawn. In the development of this SAP, the following study documents were used:

- Protocol Number (Version 1.0 Amendment 4), 17 Jan 2019
- Electronic Case Report Form (eCRF), 09 Mar 2019
- Medical Coding Guidelines (Version 2.0), 02 Nov 2017

The principles in the following guidance documents are followed in the preparation of this SAP:

- International Council for Harmonisation of Technical Requirements for Pharmaceuticals for Human Use (ICH) E3 (ICH 1995): Structure and Content of Clinical Study Reports
- ICH E6 R2 (ICH 2016): Guideline for Good Clinical Practice Integrated Addendum to ICH E6 (R1).
- ICH E9 (ICH 1998): Statistical Principles for Clinical Trials

In the event that a discrepancy is found between the descriptions in the statistical section of the protocol and this document, the description in this document supersedes the descriptions in the statistical section of the protocol. Any deviations from the final analysis plan or from what is outlined in the protocol will be discussed in the final study report.

## 3. STUDY OVERVIEW

This study is being conducted as part of a series of studies for the clinical development of APL-2. This study will be the initial exploration of APL-2 in patients with a primary diagnosis of Warm Antibody Autoimmune Hemolytic Anemia (wAIHA) who relapsed from, did not respond to, or did not tolerate at least one prior wAIHA treatment regimen (such as prednisone, rituximab, or splenectomy), or a primary diagnosis of Cold Agglutinin Disease (CAD) regardless of prior treatment history.

## 3.1 Study Objectives

The objectives of the study are to assess safety, tolerability, preliminary efficacy and pharmacokinetics (PK) of multiple subcutaneous (SC) doses of APL-2 in subjects with a primary diagnosis of wAIHA who relapsed from, did not respond to, or did not tolerate at least one prior wAIHA treatment regimen (such as prednisone, rituximab, or splenectomy), or a primary diagnosis of CAD regardless of prior treatment history.

An exploratory objective of the study is to assess the pharmacodynamics (PD) of multiple SC doses of APL-2 when administered to wAIHA and CAD patients.

## 3.2 Study Endpoints

#### 3.2.1 Primary Safety Endpoint

The primary safety endpoints of the study are the incidence and severity of treatment-emergent adverse events (TEAEs) following administration of multiple doses of SC APL-2.

### 3.2.2 Efficacy Endpoints

- Change from baseline in hemoglobin
- Number of red blood cell (RBC) transfusions during the study
- Change from baseline in absolute reticulocyte count
- Change from baseline in lactate dehydrogenase (LDH)
- Change from baseline in haptoglobin
- Change from baseline in indirect bilirubin

- APL-2 serum concentrations and PK parameters, as appropriate
- Change from baseline in Functional Assessment of Chronic Illness Therapy (FACIT) scale and the Linear Analog Scale Assessment scale (LASA) including energy level, ability to perform daily activity, and overall quality of life (QoL)

## 3.2.3 Exploratory Study Endpoints

Exploratory PD markers include:

- Complement (e.g., CH50, AH50, and C3) activity and levels
- C3 deposition on RBC cells

### 3.3 Study Design

This is a Phase II, open-label, prospective pilot study of APL-2 conducted in subjects with a primary diagnosis of wAIHA or CAD in parallel. The study will consist of up to 24 subjects, a target of 12 subjects with a primary diagnosis of wAIHA in Cohort 1 and a target of 12 subjects with a primary diagnosis of CAD in Cohort 2. Subjects will be randomized 1:1 to a 270mg or 360mg daily SC APL-2 dosage group within each cohort for up to 12 months (Part A, the Core Study Phase).

Following Day 336 and the completion of the Part A Core Study Phase, subjects will be eligible to participate in Part B, a Long-Term Extension Phase, in order to continue to receive treatment with APL-2. The Long-Term Extension Phase is described later in this section.

Through Part A (Day 336), dose escalation from 270 mg/d to 360 mg/d, or deescalation from 360 mg/d to 270 mg/d may occur after a thorough evaluation of available safety and laboratory assessment.

Safety will be assessed throughout the study; serial blood and urine samples will be collected for these assessments. Blood samples will be collected for the assessment of APL-2 PK. Additional samples for assessment of PD will also be collected.

#### Part A: Core Study Phase:

Screening will take place within 30 days prior to the start of dosing on Day 1. If needed (see inclusion criteria), *Neisseria meningitides* types A, C, W, Y and B (administered as two separate vaccines), Pneumococcal Conjugate Vaccine (PCV13) or Pneumococcal Polysaccharide Vaccine 23 (PPSV23), and Haemophilus Influenzae Type B (Hib) vaccinations will be administered prior to dosing on Day 1.

Subjects who meet all the inclusion criteria and none of the exclusion criteria will be enrolled into the study on Day 1 at a time designated by the Principal Investigator or designee (PI). During study, the first 3 daily SC doses of APL-2 (Day 1 to 3) as well as doses on Day 7 and Day 14 will be administered at the clinical site. From Day 4 to Day 336 daily doses of APL-2 will be administered off-site by a study nurse or self-administered by the subject and/or caregiver, at the subject's home, workplace, or other location convenient to the subject with the exception of those days where dosing is at the clinical site. At any time during the study, if subjects discontinue treatment, or if after the conclusion of the Part A Core Study Phase a subject does not elect to enter the Part B Long-Term Extension Phase, subjects will return to the clinical site for safety follow-up study procedures after 6 weeks, followed by final study procedures at an Exit Visit after another 6 weeks. See Study Flowchart in Section 3.3.2.

The planned length of participation in the study for each subject is at least approximately 450 days (from Day –30 through completion of the Day 420 Exit visit procedures [for subjects that do not elect to enter the Part B Long-Term Extension Phase]). Subjects that continue in the Part B Long-Term Extension Phase may continue to receive treatment indefinitely until the subject discontinues or the development program is terminated. The study duration may change in the event that the study is terminated early, additional subjects are needed, additional time is required to review safety between groups, or extended safety and PK sampling is added for a dose group (e.g. beyond Day 420).

#### Part B: Long-Term Extension Phase:

Following Visit 15 (Week 48), subjects who elect to continue in the Part B Long-Term Extension Phase will return to the site at 12-week intervals indefinitely until the subject discontinues or the development program is terminated.

Specific procedures for each visit are listed in the Study Flow Chart for the Long-Term Extension Phase in Table 2 in Section 3.3.2.

At Visit 15 (Week 48), subjects electing to enter the Part B Long-Term Extension Phase will begin an APL-2 dose regimen of APL-2 1,080 mg twice weekly (with potential to escalate to APL-2 1,080 mg every 3 days). When switching from the Part A Core Study Phase formulation and dose of APL-2 (270 mg/d or 360 mg/d) to the formulation and dose intended for use in the Long-Term Extension Phase (APL-2 1,080 mg twice weekly), subjects should return to the site for APL-2 administration training and to conduct Dose Transition Visits 1, 2 and 4 weeks after the new dose is initiated and perform the procedures outlined in Appendix Section 8.1.

Subjects who plan on continuing in the Part B Long-Term Extension Phase should be instructed to skip their daily Part A Core Study Phase Dose the day prior to Visit 15 (i.e., the subject should not self-administer APL-2 on Day 335).

**Note:** The first dose of APL-2 1,080 mg should be administered at the Visit 15 (Day 336), with Dose Transition Visits at Week 49, Week 50, and Week 52. Some subjects may enter the Part B Long-Term Extension Phase prior to the availability of the sorbitol formulation. These subjects should continue on their Part A Core Study Phase dose into the Part B Long-Term Extension Phase. These subjects will transition to the Long-Term Extension Phase dose at the next scheduled visit at which the sorbitol formulation and dose is available, and should schedule Visits T1, T2, and T3 1, 2 and 4 weeks following the visit at which the sorbitol dose is initiated. These subjects should be instructed to skip their Part A dose the day before the visit at which the APL-2 1,080 mg twice weekly dose regimen is scheduled to be initiated.

Subjects who discontinue treatment early should complete one Early Termination Follow-up Visit (ETFU) 6 weeks after discontinuation of treatment, and one Early Termination (ET) Exit Visit 6 weeks after the ETFU as outlined in Appendix 8.1.

Study Assessments align with those conducted in the Core Study Phase and are described in Section 13 of the Clinical Study Protocol (Version 1.0 Amendment 4), 17 Jan 2019.

#### 3.3.1 Sample Size Considerations

As this is a pilot study the sample size is not based on formal statistical testing. The sample size is considered sufficient to obtain useful safety, tolerability, PD, and PK data to assist the planning of future studies.

#### 3.3.2 Study Assessments Schedules

Study assessments are described in detail in Section 12.0 of the protocol (Version 1.0 Amendment 4), and summarized in Study Flow Charts for Part A and Part B in Appendix Section 8.1.

#### Version 1.0

## 4. GENERAL CONSIDERATIONS

## 4.1 Definitions

## 4.1.1 Study Day

Study Day 1 will be the day a subject takes the first dose of APL-2. Study days will be calculated as:

For events that occurred on the day of or after administration of the first APL-2 dose:

Study Day = visit date - date of first APL-2 dose + 1

For events that occurred on days before administration of the first APL-2 dose:

Study Day = visit date – date of administration of first APL-2 dose

## 4.1.2 Visit Windowing Based on Study Day

Data will be summarized and analyzed based on the list of visits specified in table below for the Part A Core Study Phase. The relative day will be used to assign analysis visit following the table below. All the records post-baseline will be assigned to an appropriate analysis visit using the following:

For the post-baseline visits, the lower and the upper bound for the analysis visit windows are defined as the midpoints of the target date of the scheduled visits. If the date of assessment falls in between the lower bound and the upper bound for a visit as specified in the schedule of assessments of the protocol, then it will be assigned to that visit. If the interval separating 2 scheduled visits is an even number of days, the middle day will be included in the lower bound of the next visit. If more than 1 record is within the same analysis visit window, the record closest to the midpoint of the interval will be used in the analysis. If 2 records are tied before and after the middle of the interval, the earlier record will be used in the analysis. If more than one assessment (including the early termination or

unscheduled assessments) falls within the same defined window, the assessment closest to the target day with non-missing data will be considered for analysis.

In listings that are presented by visit, windowed assessments that are used in the analysis tables by visit will be identified.

Part	Study Visit	Target Day	Analysis Window	Interval
Core	1	-30	<1*	NA
Study	2	1	1	1
(Part A)	3	2	2	1
	4	3	3	1
	5	7	>=4-<11	7
	6	14	11-<21	10
	7	28	21-<42	21
	8	56	42 - <70	28
	9	84	70 - < 98	28
	10	112	98 - < 126	28
	11	140	126 - < 154	28
	12	168	154 - < 196	42
	13	224	196 - < 252	56
	14	280	252 - < 308	56
	15	336	308 - < 364	56
	16 (FU)	378	364 - < 399	35
	17 (Exit)	420	399 - < 441	42

\*Must be prior to dosing if time of assessment is recorded.

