## 13.1.7 Clinical Laboratory Tests

All tests listed below will be performed as outlined in the Study Flow Chart in Section 3. In addition, laboratory safety tests may be performed at various unscheduled time points, if deemed necessary by the PI or recommended by the SMC. The clinical laboratory tests include (but are not limited to) the following:

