## 5. STATISTICAL ANALYSIS METHODOLOGY

In general, tables will be presented by randomized dose level within cohort (270 mg vs. 360 mg) and by cohort.

Tabulations for continuous data will use a standard set of descriptive statistics: number of observations available (n), mean, standard deviation (SD), median, and range (minimum, maximum).

Categorical or dichotomous data will be tabulated using frequencies (counts and percentages). The numerator and denominator for each percentage calculation will be specified in the footnotes of table shells.

Data listings will present all information recorded in eCRFs for all subjects and visits. All listings will be sorted by cohort and subject number.

Unless otherwise noted, tabulations or descriptive statistics by visit during the Part A Core Study Phase will include only scheduled visits through Visit 15 (i.e. summary statistics will not include follow-up Visits 16 and 17.

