# Apellis Pharmaceuticals, Inc.

PIOLOCOL APL2-CP-AIHA-208	
Part B Long Term Extension Statistical Analysis Plan	

Part	Study Visit	Target Day	Analysis Window	Interval
	Part B Visit 9 (Week 108)	Part B Study Day 756	Part B Study Day 714 - Part B Study Day < 798	84
Part B, cont.	Part B Visit 10 (Week 120)	Part B Study Day 840	Part B Study Day 798 - Part B Study Day < 882	84
	Part B Visit 11 (Week 132)	Part B Study Day 924	Part B Study Day 882 - Part B Study Day < 966	84
	Part B Visit 12 (Week 144)	Part B Study Day 1008	Part B Study Day 996 - Part B Study Day < 1050	84
	Part B Visit 13 (Week 156)	Part B Study Day 1092	Part B Study Day 1050 - Part B Study Day < 1134	84
	Part B Visit 14 (Week 168)	Part B Study Day 1176	Part B Study Day 1134 - Part B Study Day < 1218	84

Version 1.0

08 Nov 2022

\*For baseline assessments, must be prior to dosing.

For the purposes of the all safety and efficacy summary tables and figures by visit, there will be one result per subject per parameter per planned visit per baseline type (Part A + B Baseline and Part B Baseline). The result will be selected in the following priority within each planned subject, visit, parameter, and baseline type:

- Ensure there is an evaluable result (i.e. do not prioritize a NOT DONE assessment)
- Select the date closest to the midpoint of the analysis window per the windowing rules in Section 4.2.3
- 3) For laboratory parameters with central and local labs on the same date, if there is the same date with both local and central lab results, the central lab result is selected

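### Both SAPs let unscheduled laboratory records compete with scheduled ones on date alone, so by-visit haemoglobin and haemolysis summaries may be partly sampled on clinical events

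*SAP*

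**What the plan says.** Part A SAP Section 4.1.2 puts every post-baseline record into the windows: "All the records post-baseline will be assigned to an appropriate analysis visit using the following". Where several fall in one window it gives two selection rules in the same paragraph.

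- By interval midpoint: "the record closest to the midpoint of the interval will be used in the analysis". Ties follow: "If 2 records are tied before and after the middle of the interval, the earlier record will be used in the analysis".
- By target day, with early-termination and unscheduled records named as candidates: "unscheduled assessments) falls within the same defined window, the assessment closest to the target day with non-missing data will be considered for analysis".

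Part B SAP Section 4.2.3 repeats both rules and adds a priority list: an evaluable result first, then "Select the date closest to the midpoint of the analysis window per the windowing rules in Section 4.2.3", then central over local laboratory. Scheduled over unscheduled is not on the list.

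Part A SAP Section 5 says that by-visit statistics for Part A "will include only scheduled visits through Visit 15", and explains in the same sentence that follow-up Visits 16 and 17 are left out.

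Protocol Section 13.1.7 is one source of unscheduled values: "laboratory safety tests may be performed at various unscheduled time points, if deemed necessary by the PI or recommended by the SMC". Protocol Section 12.6.2 also lets unscheduled follow-up visits include any flow-chart procedure.

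On the windows themselves, Part A SAP Section 4.1.2 states that "the lower and the upper bound for the analysis visit windows are defined as the midpoints of the target date of the scheduled visits". Its table prints Visit 15 as Days 308 to <364 and Visit 16 as Days 364 to <399.

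**The concern.** A scheduled sample is taken because the calendar says so. An unscheduled one is taken because someone judged it necessary. If the two compete only on date, the value that enters the by-visit table can depend on how the subject was doing. Protocol Section 14.2 makes this plausible: clinically significant laboratory abnormalities are followed until they settle, with tests where appropriate to document resolution.

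Means by visit, dose group and cohort are the main efficacy output of Part A (Part A SAP Section 5.3.4). Protocol Section 7.2.1 includes two doses to help identify the better one, and the study is open-label, so discretionary sampling could differ between dose groups. With six subjects per group, one substituted value is visible in a mean.

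Two further defects sit in the same section. Its two closeness rules can select different records, and one window bound does not follow the stated midpoint rule.

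**Working it through.** **Inputs.** Target days and windows: Part A SAP Section 4.1.2. Visit tolerance of +/-7 days from Day 28 to Day 336: Protocol Table 1. Six subjects per dose group within a cohort: Protocol Section 11.3.2. The study has no power calculation to reproduce, so the SAP's own window table is the starting check.

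**1. Rebuilding the windows.** Lower bound = midpoint of adjacent target days, rounded up. This returns the printed lower bounds for Visits 6 to 15 and 17. Visit 5 is printed from Day 4 where (3+7)/2 = 5. Visit 16 is printed from Day 364 where (336+378)/2 = 357. The latter gives intervals of 56 and 35 days instead of 357-308 = 49 and 399-357 = 42.

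**2. Displacement under the target-day rule, Visit 7 on.** A scheduled sample k days off target has 2k-1 strictly closer days (none if k = 0). Assume offsets uniform over -7 to +7. The total is 2 x (1+3+5+7+9+11+13) = 98, so the mean is 98/15 = 6.53 days. Assume also one unscheduled record, uniform in the window. The chance that it is strictly closer is then:

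| Visits | Window length (days) | Mean: 6.53/length | Range: on target to 7 days off (13/length) |
|---|---|---|---|
| 7 | 21 | 31% | 0 to 62% |
| 8-11 | 28 | 23% | 0 to 46% |
| 12 | 42 | 16% | 0 to 31% |
| 13-15 | 56 | 12% | 0 to 23% |

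If ties go to the earlier record, the mean rises to 105/15 = 7.0 days. A sample 7 days late can then lose to a record on any of 14 days, and one 7 days early to any of 13.

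**3. Displacement under the midpoint rule.** Take the midpoint as (lower + upper bound)/2. It differs from the target at three visits, where even an on-target scheduled sample can lose:

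- Visit 6: (11+21)/2 = 16 against 14. Days 15-17 are closer: 3 days.
- Visit 7: (21+42)/2 = 31.5 against 28. Days 29-34 are closer: 6 days.
- Visit 12: (154+196)/2 = 175 against 168. Days 169-181 are closer: 13 days.

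The Part B SAP, whose priority list uses the midpoint, has further unequal windows. For example, its Part A Visit 15 window has midpoint (308+378)/2 = 343 against target 336.

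**4. Effect of one displaced value.** Shift in mean = difference/n. For a haemoglobin 1 to 4 g/dL below the scheduled value (assumed range), this is 1/6 to 4/6 = 0.17 to 0.67 g/dL at n = 6, and 1/12 to 4/12 = 0.08 to 0.33 g/dL at n = 12.

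**5. Reach of the Visit 15/16 bound.** The disputed days are 357-363, which is 21-27 days after a last dose on Day 336. A Visit 15 sample within tolerance (Days 329-343) beats any record on those days. The Day 378 visit within tolerance (Days 371-385) cannot fall there. For subjects who roll over, Part A data stop at Visit 15 (Part A SAP Section 4.5). The bound therefore matters only when Visit 15 is missing and a sample outside both visit windows falls in those seven days.

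**The case against.** The strongest reply is that Part A SAP Section 5 already restricts by-visit tables to scheduled visits. On that reading unscheduled records never enter them and the problem disappears. But the sentence's own explanation concerns Visits 16 and 17, and under Section 4.1.2 an unscheduled record windowed to a visit becomes that visit's data. This is an unresolved ambiguity, not a proven contradiction, and not a safeguard. The Part B SAP has no such sentence in its Section 5.

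A reader might infer that the means are sampled on disease events and are biased downwards. The documents do not support that. Section 13.1.7 names investigator judgement and committee recommendation, not haemolysis or transfusion. Section 12.6.2 also gives a non-clinical trigger, a changed PK/PD sampling schedule. No count of unscheduled draws is given. Direction is open too, since a draw after a transfusion could be high. Any average bias would need an invented episode rate, depth and recovery time. The percentages in the table apply only when an unscheduled record is already in the window.

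The reach is also limited. Under the target-day rule, from Visit 7 on, a scheduled sample within tolerance loses only to a record at least as close to target, and an on-target sample never loses.

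Finally, no inferential testing is planned, and the by-visit listings identify which windowed records were used. Individual values are listed in both SAPs and, in Part A, plotted by actual study day. Displacement can therefore be seen. That limits the harm but does not correct the tabulated means.

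**Conclusion.** The point holds as a defect in the selection rule, not as a demonstrated bias. Both SAPs allow a discretionary record to replace an available scheduled one, and Section 4.1.2 gives two closeness criteria that disagree at Visits 6, 7 and 12. Two programmers following the text could produce different haemoglobin tables.

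The displacement shares rest on uniform timing of both records. The 0.17-0.67 g/dL shift rests on an assumed 1-4 g/dL difference in one of six subjects. How often displacement would happen, and in which direction, cannot be determined from the documents.

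The Visit 15/16 bound is a plain arithmetic error in the Part A table with little practical reach. It should not be carried over to the Part B SAP, which uses different Visit 16 and 17 targets; its printed bound of 378 does follow from (336+420)/2. The consequences are confined to descriptive tables and mean plots, but the correction is cheap enough to be worth making.

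**What to change.** In Part A SAP Section 4.1.2 and Part B SAP Section 4.2.3:

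- Within a window, use the record from the scheduled visit. Use an unscheduled record only if the scheduled one is missing for that parameter. Say in the same sentence where early-termination records rank.
- Keep one closeness criterion, the target day, for choosing among any remaining candidates. Delete the midpoint version, including in the Part B priority list.
- Keep unscheduled values in the listings and in the individual plots where these are planned.

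In Part A SAP Section 5, reword the scheduled-visits sentence so that it agrees with the new rule. In the Part A window table only, print Visit 15 as 308 to <357 (49 days) and Visit 16 as 357 to <399 (42 days).

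The cost is a few sentences, two table rows and a sort key in the programs. The one small downside is that an early or late scheduled sample will be kept over an unscheduled one nearer the target day. No safety information is lost.
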